## 6.3 Time and Events Table

Part 1:			
Visit Description	Screening	Visit 1	Visit 2*
Time point	Day 0	Day 1	Day 2
Visit Window	±14 days		± 7 days
Eligibility	X		
Hgb/Hct a		X	X
Tacrolimus trough a (venipuncture-clinical lab)		X	X
Tacrolimus trough b (venipuncture- PK Core)		X	X
Tacrolimus trough (capillary, Tasso & Mitra- PK Core)		X	X
Mycophenolate trough (venipuncture- clinical lab)		X	X
Mycophenolate trough b (venipuncture- PK Core)		X	X
Mycophenolate trough (capillary, Tasso & Mitra- PK Core)		X	X
Ganciclovir concentration c (venipuncture- PK core)			
Ganciclovir concentration c (capillary, Tasso & Mitra- PK Core)			
Questionnaire		X	X

\*Visit 2 will occur if the following criteria are met:

1. Patient remains admitted to the hospital and study inclusion criteria continue to be met
2. A second standard of care tacrolimus trough concentration is ordered by the clinical team

Failure to collect samples for visit 2 will not be considered a protocol deviation.

aHgb/Hct and tacrolimus trough values from the clinical lab will be obtained from standard of care labs

bAnalysis will only be completed if leftover blood is available to be obtained from the clinical lab after completion of all ordered/standard of care labs

cAnalysis of ganciclovir will only be completed if the participant is receiving ganciclovir or valganciclovir as part of their standard of care. Addition of ganciclovir to the analysis will not change the volume of blood collected.

Visit Description	Screening	Baseline	Home collect 1	Home collect 2	Visit 3 a
Time point	Day -14	Day 0	Day 14	Day 56	Day60
Visit Window	±14 days	±14 day	±14 days	±14 days	±28 days
Informed Consent	X				
Demographics	X				
Eligibility	X				
Height/Weight	X				
Randomization		X			
Education		X			
Tacrolimus AUC (capillary- PK Core) b			X	X	
Mycophenolate AUC (capillary- PK Core) b			X	X	
Questionnaire 1		X			
Questionnaire 2				X	
Concomitant Medication Review	X				
Study Intervention c			X	X	
Drug Adherence Assessment				X	
Subject Diary			X	X	
Ecological Momentary Assessments			X	X	
Qualitative interview					X

a. Visit 3 is only applicable to participants selected using maximum variation purposive sampling

b. Consists of 4 collection events over 8 hours on each occasion (time 0, 1 hr, 4hr, and 8hr after the morning dose of tacrolimus and mycophenolate)

c. Text messaging will begin 48 hours prior to the sample collection event and continues for 48 hours after sample collection

## 7.0 ADVERSE EVENTS

This is a pharmacokinetic study, but safety data will be collected on adverse and serious adverse events.

### 7.1 Adverse Event Reporting Requirements

Since the responsibility of the management of the patient's transplant regimen is retained by the health care providers at the University of Michigan Transplant Center and not dictated by the study protocol, deaths and hospitalizations will typically not be study related. Serious adverse events (SAEs) and adverse events (AEs) that are related to the participant's kidney transplant or other chronic disease conditions are not unanticipated and therefore will not be considered reportable to the IRB. For the sake of our study purposes and outcomes we will track SAEs and AEs related to study participation.

Adverse event data will be reviewed by the project leadership team and will be summarized in reports quarterly. Non-serious (mild/moderate) adverse event data will be reported to the IRB in annual renewals. SAEs related to study participation will be reported to the IRB within 7 calendar days of identification by the study team. A privacy violation or breach of confidentiality will be reported to the IRB within 7 calendar days and to the Corporate Compliance office within 24 hours of identification.

Definition of Adverse Events (AEs): AEs that are of particular interest to our study and that we will specifically track include problems associated with capillary sampling (infection, bruising, and bleeding at the site of lancet puncture) and text message communication (privacy breach). Capillary sampling AEs will be assessed at 48 hours after collection via text message requesting patients to self-report (Table 1). We will also assess for hospitalizations, urgent care/emergency room visits, and death. These events will be collected via electronic record review or self-report.

The severity or grade of an adverse event may be measured using the following definitions:

Mild: Noticeable to the subject, but does not interfere with subject's expected daily activities, usually does not require additional therapy or intervention, dose reduction, or discontinuation of the study.

Moderate: Interferes with the subject's expected daily activities, may require some additional therapy or intervention but does not require discontinuation of the study.

Severe: Extremely limits the subject's daily activities and may require discontinuation of study therapy, and/or additional treatment or intervention to resolve.

The investigator or co-investigator is responsible for assignment of attribution.

Definite – The AE is clearly related to the study intervention.

Probable – The AE is likely related to the study treatment/intervention.

Possible – The AE may be related to the study treatment/intervention.

Unlikely – The AE is doubtfully related to the study treatment/intervention.

Unrelated – The AE is clearly NOT related to the study treatment/intervention.

## 7.2 Reporting of Unanticipated Problems

There are types of incidents, experiences, and outcomes that occur during the conduct of human subjects research that represent unanticipated problems but are not considered adverse events. For example, some unanticipated problems involve social or economic harm instead of the physical or psychological harm associated with adverse events. In other cases, unanticipated problems place subjects or others at increased risk of harm, but no harm occurs. Unanticipated problems that are related to the study and indicate risk to subjects and are not also SAEs will be reported to the IRB within 14 calendar days.

Unanticipated problem: Per FDA Procedural Guidance for Clinical Investigators, Sponsors, and IRBs (January 2009), an unanticipated problem is defined as a serious problem that has implications for the conduct of the study (requiring a significant and usually safety-related, change in the protocol (such as revising inclusion/exclusion criteria or including a new monitoring requirement), informed consent or investigator's brochure).

Upon becoming aware of any incident, experience, or outcome (not related to an adverse event) that may represent an unanticipated problem, the investigator should assess whether the incident, experience, or outcome represents an unanticipated problem. The incident, experience, or outcomes is considered unanticipated if it meets all of the following criteria:

1. Unexpected (in terms of nature, severity, or frequency);
2. Related or possibly related to participation in the research; and
3. Suggests that the research places subjects or others at a greater risk of harm than was previously known or recognized.

Unanticipated problem Reporting: Per 21 CFR 312.66, 312.53 (c)(1)(vii), and 56.108(b)(1), should an Unanticipated problem occur during the investigation, the investigator will promptly report all unanticipated problems involving risks to human subjects or others to the IRB.

### 7.3 Reporting of Pregnancy

Pregnancy status will not be assessed during this study. The interventions of this study are not expected to cause pregnancy-related harm.

Participants enrolled in this study are receiving mycophenolate as the standard of care and not as a study intervention. Women of childbearing potential receive education on the risk of mycophenolate during pregnancy at the time of therapy initiation as mandated by the US Food and Drug Administration (FDA) Mycophenolate Risk Evaluation and Mitigation Strategy (REMS). Participants of childbearing potential will be provided with reinforcement of the REMS education during the informed consent process. If pregnancy occurs and mycophenolate is discontinued at the discretion of the treating physician, the study intervention will also be discontinued as stated in section 5.4.

## 8.0 DEVICE INFORMATION

The Tasso OnDemand is a sterile, disposable, integrated capillary blood collection device, including a lancet assembly and a detachable reservoir for the collection of blood.

The Tasso-M20 is used for the self-collection and storage of capillary blood from minimally trained users and shipping to a central laboratory for analysis. This configuration is available commercially and is registered with the FDA as a class 1 blood collection and container system. Tasso, Inc has validated the device utilizing the safety, sterility, packaging, and biocompatibility test methods required by the FDA for a medical device that interfaces with the body for less than 24 hours.

The mechanism is very simple to operate and enables the collection of a blood sample at the press of button. The device is placed on the skin of the upper arm and remains in position using an adhesive backing. The device is actuated by pressing the central button, causing an internal spring to contract and a plunger, containing a single 16-gauge stainless-steel lancet which penetrates 2.5mm into the skin. Upon actuation of the device, the lancet penetrates the skin, is immediately retracted (does not remain deployed for the whole wear time), and locks in an inactive position to prevent re-use. The lancet puncture causes blood to pool on the surface of the skin, which is further enhanced by the small amount of vacuum (~40 kPa). The base of the device is designed to collect the blood pooling on the surface of the skin and channel the blood into a detachable reservoir. The blood collection is stopped after the blood reaches an indicator on the reservoir (fill window for the dried blood configuration for a total sample of 80 $\mu$ L).

Risk analysis has been performed in accordance with ISO 14971. Risk Management Report Risks associated with use of the Tasso OnDemand are expected to be similar to those of other blood collection device, including risks related to the infection, pain and loss of sample integrity. The 40 kPa vacuum enhances the blood draw while reducing negative effects on the skin, such as hematomas or marks. Typically, a small mark, similar to those left by fingerstick devices, remains on the skin for 24-48 hours. Rarely, slight bruising is observed that does not lead to other negative consequences. The device presents minimal risk to the subjects in the study as the procedures involved are common lancet punctures. The device has been applied on over 50,000 subjects since 2014 without any adverse events recorded.

The Tasso-M20 is supplied to participants as part of a kit including the device in a sterile pouch, alcohol pad, bandage, instruction sheet, specimen bag/return pouch with moisture absorbing packs, and box for mailing. Each device is single use.

The Mitra is a separate specimen collector for the storage and transport of biological fluids. To obtain the capillary blood, a sterile single use, contact activated safety lancet will be used.

## 9.0 STATISTICAL CONSIDERATIONS

This section presents a summary of the planned statistical analyses.

### 9.1 Study Design/Study Outcome Measures

Part 1: This study is a clinical validation for the comparison of bioanalytical methods.

Part 2: This study is a prospective, randomized, pilot evaluation of a text messaging intervention to facilitate self-collection of dried blood samples for tacrolimus and mycophenolate therapeutic drug monitoring.

### 9.2 Primary Objective (Part 2)

9.2.1 To compare the effect of bidirectional text communication on adherence to and accuracy of home-based AUC collection versus unidirectional text

reminders in kidney transplant recipients receiving tacrolimus and mycophenolate.

**Primary Outcome Measure:** successful home-based TDM defined as the timely receipt of samples that are adequate for pharmacokinetic analysis.

Samples will be considered timely if post-marked within 48 hours of planned sample collection. Samples will be considered adequate for analysis if all 4 sample collections are documented within the designated sample collection window.

### **9.3 Secondary Objectives (Part 1)**

9.3.1 To assess the bioanalytical agreement of two sample collection methods (dried blood spot and venipuncture) as measured by Liquid Chromatography with tandem mass spectrometry (LC-MS/MS).

**Secondary Outcome Measure:** difference between drug concentrations measured from concurrent dried blood spot and venipuncture samples.

### **9.4 Exploratory Objectives**

9.4.1 To evaluate the predictive performance of a mycophenolate matrix conversion equation. (Part 1)

**Exploratory Outcome Measure:** median percentage predictive error and median absolute predictive error

9.4.2 To assess the bioanalytical agreement of two sample collection methods (dried blood spot and venipuncture) as measured by LC-MS/MS assay at the University of Michigan PK Core and Michigan Medicine Clinical laboratory. (Part 1)

**Exploratory Outcome Measure:** difference between drug concentrations measured from the two LC-MS/MS assays.

9.4.3 To evaluate participant characteristics based on the Theoretical Domains Framework associated with successful home-based TDM. (Part 2)

**Exploratory Outcome Measure:** The relationship between patient characteristics and successful home-based TDM

### **9.5 Sample Size and Accrual**

Part 1: The expected LC-MS/MS assay coefficient of variation (CV) of >5% with a range ratio of >25 requires 40 participants with 80 paired dried and venous samples (2 pairs from each participant) to clinically validate the assay, including validation of the anticipated

mycophenolate conversion factor. To account for participants unwilling to provide additional samples, up to 90 participants may be enrolled.

Part 2: Compared to the previous rate for successful sample collection of 55% reported in the literature, the selected sample size of 45 participants will provide this pilot study >90% power to detect a 25% difference in successful sample collection (anticipated overall success of 80% in both groups).

The sample size is also adequate to assess the secondary and exploratory outcomes. Additionally, the 45 participants will provide 80% power for a 95% confidence interval to identify a 10-point difference in the absolute prediction error (APE) between AUC calculated from all 4 samples and estimates using different sampling combinations for tacrolimus. Finally, the convenience sample of the included patients will be used for the quantitative analysis to provide preliminary data describing the relationships between Theoretical Domain constructs and successful competition of home-based TDM. Qualitative interviews will be conducted with a minimum of 10 participants or until data saturation is reached.

Subjects will be considered evaluable if they complete the baseline survey and attempt to complete at least 1 home AUC collection.

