In transplantation, existing literature suggests patients can collect dried blood samples at home, are generally satisfied with the procedure, and are willing to provide more samples with this method, particularly if it can replace venipuncture or reduce clinic visits. However, data are primarily limited to non-US populations and lack a robust framework to ensure a complete understanding of the behavior. Further, preliminary data shows that adherence to the collection is low, with 42-55% completion rates without intervention. Additional work is needed to develop strategies to increase adherence to monitoring. Text messaging reminders have been demonstrated to improve medication adherence and other positive health behaviors. Text messages are low cost with minimal infrastructure requirements and more accessible to patients with a low technology literacy or in rural areas with low cellular bandwidth. In a 2015 survey of kidney transplant recipients, 96% owned a mobile phone and 74% used text messaging compared to 47% who used apps. Text messaging is the preferred method of health communication in adolescent and young adult recipients. The use of text messaging offers the potential to be a viable tool to increase adherence to home-based TDM for most of the transplant population.

Our contributions are expected to develop a patient-centric strategy to allow frequent, longitudinal, minimally invasive sample collection for bioanalysis of immunosuppression and other supportive therapy drug concentrations. These contributions will be significant because they are expected to overcome many barriers that have limited progress towards enhanced precision pharmacotherapy in transplantation. The methods will facilitate decentralized multicenter clinical trials by reducing costs and simplifying biorepositories to achieve the sample sizes necessary to conclusively establish the benefits of expanded TDM on long-term patient outcomes. Further, improving the technical capacity of home-based sampling to substitute for frequent phlebotomy will improve patients' quality of life by allowing increased autonomy to self-monitor by collecting blood samples at home.

Figure 1.  
Tasso-M20 Device

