### 2.1 Primary Objective (Part 2)

2.1.1 To compare the effect of bidirectional text communication on adherence to and accuracy of home-based AUC collection versus unidirectional text reminders in kidney transplant recipients receiving tacrolimus and mycophenolate.

**Primary Outcome Measure:** successful home-based TDM defined as the timely receipt of samples that are adequate for pharmacokinetic analysis.

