#### **4.3 Randomization**

Part 1: no randomization

Part 2: 45 patients who meet the inclusion criteria will be randomized in a 1:2 allocation ratio to receive one of two text messaging interventions stratified by age  $\geq$  or  $<$  65 years. The randomization list will be generated by the study biostatistician.

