### **5.0 INTERVENTION PLAN (PART 2 ONLY)**

#### **5.1 Intervention Administration**

All participants will self-collect dried blood samples using the Tasso-M20 device at the specified intervals. Each self-collection will obtain up to 80 $\mu$ L of capillary blood (4 x 20 $\mu$ L samples). Dried blood samples will be obtained concurrently with venipuncture samples at study visit 1 and 2. The participants will self-collect dried blood samples in their home environment for AUC analysis on two occasions. Self-collected samples will be collected immediately prior to the morning dose of tacrolimus and mycophenolate (C0) and at approximately 1, 4, and 8 hours after the dose.

To promote adherence and accurate sample collection, participants will be randomized to 1 of 2 automated text messaging interventions. Messages will be sent using a commercial web to text messaging gateway (Twilio). Twilio will be enabled in the REDCap project. Message replies will be stored in REDCap not on Twilio servers. The request inspector will be disabled in Twilio as required by REDCAP for HIPPA compliance. No protected health information (PHI) or identifying information will be in messages (See Table 1 for message content). A control group without messages will not be used due to preexisting knowledge of low rates of completion without intervention.

Anticipated sample collection dates and times will be discussed with the participant during the baseline visit to trigger messaging timeline. If a response is received to any message not using an expected keyword, the recipient will receive a text message that the entry is an invalid value and to try again. The participants will be educated to contact the study team with any issues.

The participant will be able to opt-out of messages with the standard keywords: “cancel”, “stop”, “end”, “quit”, “stopall”, and “unsubscribe.” In response they will receive the following message: “You have successfully been unsubscribed. You will not received any more messages from this number. Someone from the study team will contact you to follow up. Reply START to resubscribe.

In response to the keywords “help” or “info” participants will receive the following message: “For help, please call the study team [contact] or email [[contact]](mailto:[contact]).”

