## 9.6 Data Analyses Plan

9.6.1 **Primary Objective**- To compare the effect of bidirectional text communication on adherence to and accuracy of home-based AUC collection versus unidirectional text reminders in kidney transplant recipients receiving tacrolimus and mycophenolate.

**Primary Outcome Measure:** successful home-based TDM defined as the timely receipt of samples that are adequate for pharmacokinetic analysis.

Samples will be considered timely if post-marked within 48 hours of planned sample collection. Samples will be considered adequate for analysis if all 4 sample collections are documented within the designated sample collection window.

The primary endpoint between the study groups will be compared using the chi-squared test. Comparisons of demographic and clinical characteristics between successful and unsuccessful participants will be made. A multivariable logistic regression will also be completed, where the primary independent variable is the study group, controlled for age, sex, and time since transplant. The latter analyses will explore factors that may impact adherence to sampling.

9.6.2 **Secondary Objectives** - To assess the bioanalytical agreement of two sample collection methods (dried blood spot and venipuncture) as measured by Liquid Chromatography with tandem mass spectrometry (LC-MS/MS).

Secondary Outcome Measure: difference between drug concentrations measured from concurrent dried blood spot and venipuncture samples.

Passing-Bablok regression will be used to measure the linear relationship between the drug concentrations obtained in venipuncture and dried capillary samples. Bland-Altman plots will be used to assess agreement and estimate bias. Acceptance criteria will be in accordance with the Food and Drug Administration (FDA) Bioanalytical Method Validation. Drug concentrations from dried blood spots must be within  $\pm 15\%$  of venipuncture value in  $\geq 67\%$  of samples.

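### The >90% power in section 9.5 belongs to a pooled comparison with a 55% literature rate that section 9.6 does not plan; the planned between-arm chi-squared test has no power or precision statement

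*Combined protocol and SAP*

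**What the plan says.** Section 9.5 sizes Part 2 in one sentence. It opens with its comparator, "Compared to the previous rate for successful sample collection of 55% reported in the literature", states that "the selected sample size of 45 participants will provide this pilot study >90% power to detect a 25% difference in successful sample collection", and closes with the expectation in brackets: "anticipated overall success of 80% in both groups".

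The question and the analysis are set elsewhere:

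- Section 2.1, repeated in 9.2 and 9.6.1, gives the primary objective: "To compare the effect of bidirectional text communication on adherence to and accuracy of home-based AUC collection versus unidirectional text reminders".
- Section 4.3 has 45 patients "randomized in a 1:2 allocation ratio to receive one of two text messaging interventions stratified by age", which is about 15 and 30. It does not say which intervention gets the larger arm.
- Section 9.6.1 gives the primary test: "The primary endpoint between the study groups will be compared using the chi-squared test". It adds comparisons of successful with unsuccessful participants and a logistic regression with study group as the main variable.
- Section 1.2 shows where the 55% comes from: "preliminary data shows that adherence to the collection is low, with 42-55% completion rates without intervention".
- Section 5.1 rules out an arm of that kind: "A control group without messages will not be used due to preexisting knowledge of low rates of completion without intervention".

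Neither section 9.6 nor the synopsis plans a test or confidence interval for the success rate against 55%. The other Part 2 power statement in 9.5 concerns the absolute prediction error of AUC estimates. The general claim of adequate size in 9.5 covers only secondary and exploratory outcomes.

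**The concern.** The comparison used to justify the sample size is not in the analysis plan, and the comparison in the analysis plan has no justification. Both arms receive texts, so neither represents the no-intervention condition behind the 55%, and a between-arm test cannot address it. For the arm comparison itself, 9.5 anticipates the same success rate in both groups, which leaves the primary test no anticipated effect to detect.

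The >90% is the only power figure given for successful collection. It is worded as a 25-point difference and sits beside a reference to both groups, so it is easily taken to cover the randomised comparison. A non-significant result could then be reported as ruling out a 25-point benefit of bidirectional texting. Meanwhile the question that 45 participants can answer with good power has no prespecified analysis.

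**Working it through.** **Inputs from the documents.** N = 45, reference rate 55%, anticipated rate 80% in both groups, claimed power >90% (all 9.5); allocation 1:2, so 15 and 30 (4.3); between-arm chi-squared test (9.6.1).

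**Assumptions, because the documents do not state them.** Two-sided alpha of 0.05, one success or failure per participant, and Pearson chi-squared without continuity correction unless noted.

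**Step 1: reproduce the stated figure.** Take all 45 participants together, p0 = 0.55 and p1 = 0.80.

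- Normal approximation: power = Φ[(p1 − p0 − 1.96·√(p0(1 − p0)/n)) / √(p1(1 − p1)/n)] = Φ[(0.25 − 1.96 × 0.0742) / 0.0596] = Φ(1.755) = 96.0%.
- Exact binomial: the smallest r with P(X ≥ r | 45, 0.55) ≤ 0.025 is 32, with upper tail 0.0201. Power = P(X ≥ 32 | 45, 0.80) = 94.8%.

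Both agree with >90%.

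**Step 2: try to read the figure as a between-arm comparison.** At 55% against 80%, the two-sided normal approximation gives 36% to 43% across splits of 15/30, 30/15 and 22/23. One-sided testing gives 50% to 56%. Counting the two collections per participant as 90 independent units gives 66% to 72%. None of these reaches 90%, so only the pooled reading reproduces the claim.

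**Step 3: power of the planned test.** Sum Bin(15, p1) × Bin(30, p2) over all 2×2 tables that the test rejects. For a 25-point gap with overall success at 80%, solve (15·p1 + 30·p2)/45 = 0.80. If the arm of 15 is lower, p1 = 0.80 − (2/3)(0.25) = 63.3% and p2 = 88.3%. If it is higher, p1 = 96.7% and p2 = 71.7%.

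| Arm of 15 vs arm of 30 | Pearson | Continuity-corrected | Fisher |
|---|---|---|---|
| 55% vs 80% | 43.4% | 30.0% | 34.7% |
| 80% vs 55% | 37.9% | 25.8% | 30.5% |
| 63.3% vs 88.3% | 50.1% | 37.4% | 43.6% |
| 96.7% vs 71.7% | 58.2% | 33.0% | 45.5% |
| 70% vs 95% | 62.0% | 42.9% | 59.3% |
| 95% vs 70% | 55.1% | 32.4% | 43.7% |
| 75% vs 100% | 92.0% | 53.9% | 76.4% |
| 100% vs 75% | 65.2% | 32.6% | 48.6% |
| 80% vs 80% | 5.0% | 1.8% | 3.0% |

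Of the 25-point gaps examined, only one passes 90%: the uncorrected test with the larger arm at 100%. The last row is the plan's own expectation, and there the test rejects only at its type I error rate.

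**Step 4: detectable difference and precision.** With overall success at 80%, the uncorrected test reaches about 80% power at a gap of about 36 points if the arm of 15 is lower (56% vs 92%), or about 30 points if it is higher (99.7% vs about 70%). At 80% in both arms, the 95% confidence interval half-width for the difference is 1.96·√(0.16/15 + 0.16/30) = 1.96 × 0.1265 = 24.8 points.

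For scale only: at 1:2 allocation, detecting 55% against 80% would need about 120 to 125 participants for 80% power and 159 to 164 for 90%.

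**The case against.** The strongest reply is that Part 2 is labelled a pilot throughout and need not be powered for the arm comparison. That is right, and nothing here asks for more participants. But 9.5 chose to state a power, and pilot status does not transfer it to the planned test.

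A second reply is that 9.5 names its literature comparator and assumes equal arms, so a careful reader can see what the >90% refers to, and no passage says that non-significance would show equivalence. This is fair: the misreading is a risk, not something the documents assert. It also confirms the mismatch, because a reader who understands the sentence correctly then finds no matching analysis in 9.6.

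Three limits stand:

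- Section 9 calls itself a summary, and Appendix A mentions a statistical analysis plan that may be updated. The supportable statement is that the documents as they stand plan no test against 55%.
- Section 9.5 does not use the word pooled. That reading is an inference, though it is the only one tried that reproduces the figure.
- The uncorrected Pearson figures are mostly the most favourable of the three tests. With 80% success in both arms, about 9 failures are expected, only 3 of them in the arm of 15, which is thin for that test.

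The unit of success (participant or collection) is also undefined. Step 2 shows that a per-collection count does not rescue the >90%.

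**Conclusion.** The concern holds, and section 9.5 is wrong as written for the primary analysis. The >90% is sound for 45 pooled participants against a fixed 55% (94.8% exact). It does not describe the between-arm test, whose uncorrected power for a 25-point gap lies between 38% and 62% in the scenarios with no arm at 100%. The continuity-corrected test gives 26% to 43% in the same scenarios and Fisher's test 31% to 59%. Under the plan's own expectation of equal rates, the arm difference would be estimated to within about ±25 points.

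The exact percentages depend on the assumed two-sided 0.05, the 15/30 split, one outcome per participant and the chi-squared variant. The mismatch between 9.5 and 9.6.1 does not depend on them. It should be corrected because it concerns the primary analysis, even though the correction is small.

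**What to change.** 1. In 9.5, say that the >90% refers to the success rate of all 45 participants against 55%. Then either add a one-sample exact binomial test with its 95% confidence interval to 9.6.1 as a supportive analysis, or label the 55% comparison as feasibility rationale only.
2. In 9.5, state the power of the between-arm test with its assumed rates, alpha, sidedness, unit of analysis and test variant. For an uncorrected chi-squared at two-sided 0.05 with 15 and 30 participants, that is about 38% to 43% at 55% against 80%, and about 50% to 58% for a 25-point gap at overall 80%. With Fisher's test the ranges are about 30% to 35% and 44% to 46%; with continuity correction, about 26% to 30% and 33% to 37%. Add the expected half-width of about ±25 points at 80% in both arms.
3. In 9.6.1, report the arm effect as a risk difference with a 95% confidence interval, and say that a non-significant result is not evidence of equivalence. This goes beyond repairing the inconsistency, but it guards against the misreading.

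The cost is protocol wording, plus one supportive test if that option is taken. The sample size does not change. The stated power for the randomised comparison becomes less favourable.
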